Appendix F. SCORing Atopic Dermatitis (SCORAD) Example

The SCORAD is a tool used in clinical research and clinical practice that was developed to standardize the evaluation of the extent and severity of AD.²⁰

Body Area Affected:

The extent of AD is assessed as a percentage of each defined body area. To help in determining this extent, the sites affected by eczema are shaded on a drawing of a body. The rule of 9 is used to calculate the affected area (A) as a percentage of the whole body:

- Head and neck 9%
- Upper limbs 9% each
- Lower limbs 18% each
- Anterior trunk 18%
- Back 18%
- Genitals 1%

The score for each area is added up. The total area is 'A,' which has a possible maximum of 100%.

Symptom Severity:

A representative area of eczema is selected. In this area, the intensity of each of the following 6 specific symptoms is assessed as none (0), mild (1), moderate (2) or severe (3).

- Redness
- Swelling
- Oozing/crusting
- Scratch marks
- Skin thickening (lichenification)
- Dryness (this is assessed in an area where there is no inflammation)

The scores for these 6 specific symptoms should be added, for a maximum of 18 total points, assigned as "B" in the overall SCORAD calculation.

Subjective Symptoms:

Subjective assessment of itch and sleeplessness is recorded for each symptom by the subject on a visual analogue scale (VAS), where 0 is no itch (or sleeplessness) and 10 is the worst imaginable itch (or sleeplessness), with a maximum possible score of 20. This parameter is assigned as "C" in the overall SCORAD calculation.

Visual analog scale
(average for the last
3 days or nights)

PRURITUS (0to10)		0	10
SLEEP LOSS (0to10)			

(10 cm in length)

SCORAD Calculation:

The SCORAD is calculated as: $A/5 + 7B/2 + C$.

Appendix G. Dermatology Life Quality Index (DLQI) Example

DERMATOLOGY LIFE QUALITY INDEX

Hospital No: _____ Date: _____
 Name: _____ Score: DLQI
 Address: _____ Diagnosis: _____

The aim of this questionnaire is to measure how much your skin problem has affected your life OVER THE LAST WEEK. Please tick one box for each question.

- | | | | |
|----|---|--|---------------------------------------|
| 1. | Over the last week, how itchy, sore, painful or stinging has your skin been? | Very much 
A lot 
A little 
Not at all  | |
| 2. | Over the last week, how embarrassed or self conscious have you been because of your skin? | Very much 
A lot 
A little 
Not at all  | |
| 3. | Over the last week, how much has your skin interfered with you going shopping or looking after your home or garden ? | Very much 
A lot 
A little 
Not at all  | Not relevant  |
| 4. | Over the last week, how much has your skin influenced the clothes you wear? | Very much 
A lot 
A little 
Not at all  | Not relevant  |
| 5. | Over the last week, how much has your skin affected any social or leisure activities? | Very much 
A lot 
A little 
Not at all  | Not relevant  |
| 6. | Over the last week, how much has your skin made it difficult for you to do any sport ? | Very much 
A lot 
A little 
Not at all  | Not relevant  |
| 7. | Over the last week, has your skin prevented you from working or studying ? | Yes 
No  | Not relevant  |
| | If "No", over the last week how much has your skin been a problem at work or studying ? | A lot 
A little 
Not at all  | |

8. Over the last week, how much has your skin created problems with your **partner** or any of your **close friends** or **relatives**? Very much
A lot
A little
Not at all Not relevant
9. Over the last week, how much has your skin caused any **sexual difficulties**? Very much
A lot
A little
Not at all Not relevant
10. Over the last week, how much of a problem has the **treatment** for your skin been, for example by making your home messy, or by taking up time? Very much
A lot
A little
Not at all Not relevant

Please check you have answered EVERY question. Thank you.

©AY Finlay, GK Khan, April 1992 www.dermatology.org.uk, this must not be copied without the permission of the authors.

Appendix H. Pruritus (Itch) Numerical Rating Scale (NRS) Example

Pruritus/Itch Numeric Rating Scale

© AbbVie Inc., 10June2016 24hr V1

Appendix I. Medical Outcomes Study (MOS) Sleep Scale-Revised Example

Your Sleep

For each of the following questions, please mark an in the one box that best describes your answer.

1. How long did it usually take for you to fall asleep during the past 4 weeks?

0-15 minutes	16-30 minutes	31-45 minutes	46-60 minutes	More than 60 minutes
▼	▼	▼	▼	▼
 1	 2	 3	 4	 5

2. On the average, how many hours did you sleep each night during the past 4 weeks?

Write in number of hours per night:

3. How often during the past 4 weeks did you...

	All of the time	Most of the time	Some of the time	A little of the time	None of the time
	▼	▼	▼	▼	▼
a	feel that your sleep was not quiet (moving restlessly, feeling tense, speaking, etc., while sleeping)?				
	 1	 2	 3	 4	 5
b	get enough sleep to feel rested upon waking in the morning?				
	 1	 2	 3	 4	 5
c	awaken short of breath or with a headache?				
	 1	 2	 3	 4	 5
d	feel drowsy or sleepy during the day?				
	 1	 2	 3	 4	 5
e	have trouble falling asleep?				
	 1	 2	 3	 4	 5

How often during the past 4 weeks did you...

	All of the time	Most of the time	Some of the time	A little of the time	None of the time
f					
awaken during your sleep time and have trouble falling asleep again?.....	 1.....	 2.....	 3.....	 4.....	 5
g					
have trouble staying awake during the day?.....	 1.....	 2.....	 3.....	 4.....	 5
h					
snore during your sleep?.....	 1.....	 2.....	 3.....	 4.....	 5
i					
take naps (5 minutes or longer) during the day?.....	 1.....	 2.....	 3.....	 4.....	 5
j					
get the amount of sleep you needed?.....	 1.....	 2.....	 3.....	 4.....	 5

Copyright, 1986, RAND.
MOS 12-Item Sleep Scale – Revised 2010
United States (English)

Appendix J. Patient Oriented Eczema Measure (POEM) Example

POEM for self-completion

Patient Details: _____

Date: _____

Please circle one response for each of the seven questions below about your eczema. Please leave blank any questions you feel unable to answer.

1. Over the last week, on how many days has your skin been itchy because of your eczema?

No days 1-2 days 3-4 days 5-6 days Every day

2. Over the last week, on how many nights has your sleep been disturbed because of your eczema?

No days 1-2 days 3-4 days 5-6 days Every day

3. Over the last week, on how many days has your skin been bleeding because of your eczema?

No days 1-2 days 3-4 days 5-6 days Every day

4. Over the last week, on how many days has your skin been weeping or oozing clear fluid because of your eczema?

No days 1-2 days 3-4 days 5-6 days Every day

5. Over the last week, on how many days has your skin been cracked because of your eczema?

No days 1-2 days 3-4 days 5-6 days Every day

6. Over the last week, on how many days has your skin been flaking off because of your eczema?

No days 1-2 days 3-4 days 5-6 days Every day

7. Over the last week, on how many days has your skin felt dry or rough because of your eczema?

No days 1-2 days 3-4 days 5-6 days Every day

POEM for self-completion

How is the scoring done?

Each of the seven questions carries equal weight and is scored from 0 to 4 as follows:

No days	= 0
1-2 days	= 1
3-4 days	= 2
5-6 days	= 3
Every day	= 4

Note:

- If one question is left unanswered this is scored 0 and the scores are summed and expressed as usual out of a maximum of 28
- If two or more questions are left unanswered the questionnaire is not scored
- If two or more response options are selected, the response option with the highest score should be recorded

What does a poem score mean?

To help patients and clinicians to understand their POEM scores, the following bandings have been established (see references below):

• 0 to 2	= Clear or almost clear
• 3 to 7	= Mild eczema
• 8 to 16	= Moderate eczema
• 17 to 24	= Severe eczema
• 25 to 28	= Very severe eczema

Do I need permission to use the scale?

Whilst the POEM scale is protected by copyright, it is freely available for use and can be downloaded from: www.nottingham.ac.uk/dermatology
We do however ask that you register your use of the POEM by e-mailing [contact] with details of how you would like to use the scale, and which countries the scale will be used in.

References

Appendix K. Asthma Symptoms Questionnaire Example

Appendix L. Daytime Nasal Symptoms Questionnaire Example

Appendix M. Atopic Dermatitis Symptom Scale (ADerm-SS) Questionnaire Example

**Appendix N. Atopic Dermatitis Impact Scale (ADerm-IS) Questionnaire
Example**

**Appendix O. Patient Global Impression of Severity (PGIS) Questionnaire
Example**

Appendix P. Local Canada Requirements

Section 5.2.1, Inclusion Criteria

10. If female of childbearing potential, must be practicing at least two reliable methods of contraception (one highly effective method combined with one effective method, refer to Section 5.2.4), that are effective from Study Day 1 through at least 30 days after the last dose of study drug.
11. If male, and subject is sexually active with the female partner(s) of childbearing potential, he must agree, from Study Day 1 through 30 days after the last dose of study drug, to practice the protocol-specified contraception (refer to Section 5.2.4).

Section 5.2.4, Contraception Recommendations

Contraception Recommendation for Females

A woman who is postmenopausal or permanently surgically sterile (bilateral oophorectomy, bilateral salpingectomy or hysterectomy) is not considered to be a woman of childbearing potential and is not required to follow contraception recommendations.

Postmenopausal is defined as:

- Age \geq 55 years with no menses for 12 or more months without an alternative medical cause; or
- Age $<$ 55 years with no menses for 12 or more months without an alternative medical cause AND an FSH level $>$ 40 mIU/L.

A woman who does not meet the definition of postmenopausal or permanently surgically sterile is considered of childbearing potential and is required to use two forms of contraception. This includes one form of highly effective contraception and one effective method of contraception. That is effective from Study Day 1 (or earlier) through at least 30 days after the last dose of oral study drug.

- Highly effective methods:
 - Hormonal contraceptives started at least 2 months prior to randomization (e.g., combined [estrogen and progestogen containing] [oral contraceptives, patch, vaginal ring, injectables, and implants]);
 - Intrauterine device (IUD) or intrauterine system (IUS);
 - Vasectomy and tubal ligation.
- Effective methods:
 - Barrier methods of contraception (e.g., male condom, female condom, cervical cap, diaphragm, contraceptive sponge)
 - Note: The proper use of diaphragm or cervical cap includes use of spermicide and is considered one barrier method. The cervical cap and contraceptive sponge are less effective in parous women. The use of spermicide alone is not considered a suitable barrier method for contraception. When used consistently and correctly, "double barrier" methods of contraception (e.g., male condom with diaphragm, male condom with cervical cap) can be used as an effective alternative to the highly effective contraception methods described above. Male and female condoms should not be used together as they can tear or become damaged.

Contraception Recommendation for Males

For a male subject who has a female partner who is postmenopausal or permanently sterile, no contraception is required.

A male subject who is sexually active with female partner(s) of childbearing potential must agree from Study Day 1 through 30 days after the last dose of oral study drug to practice contraception with:

- Condom use and female partner(s) using at least one of the highly effective contraceptive methods (as defined in the protocol for female study subjects of childbearing potential).

Additionally, male subjects must agree not to donate sperm from Study Day 1 through 30 days after the last dose of oral study drug.

Male subjects are responsible for informing his partner(s) of the risk of becoming pregnant and for reporting any pregnancy to the study doctor. If a pregnancy occurs, a partner authorization form requesting pregnancy outcome information will be requested from the pregnant partner.

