 14. History of an allergic reaction or significant sensitivity to constituents of the study drugs and/or other products in the same class.
 15. History of clinically significant (per Investigator's judgment) drug or alcohol abuse within the last 6 months preceding the Baseline Visit.
 16. Female subject who is pregnant, breastfeeding or is considering becoming pregnant during the study or for approximately 30 days after the last dose of study drug.

17. Male subject who is considering fathering a child or donating sperm during the study or for approximately 30 days after the last dose of study drug.
18. Laboratory values meeting the following criteria within the Screening period prior to the first dose of study drug (Baseline Visit):
 - Serum aspartate transaminase (AST) $> 2 \times$ ULN;
 - Serum alanine transaminase (ALT) $> 2 \times$ ULN;
 - Estimated glomerular filtration rate (GFR) by simplified 4-variable Modification of Diet in Renal Disease (MDRD) formula < 40 mL/min/1.73 m²;
 - Total white blood cell count (WBC) $< 2,500/\mu\text{L}$;
 - Absolute neutrophil count (ANC) $< 1,500/\mu\text{L}$;
 - Platelet count $< 100,000/\mu\text{L}$;
 - Absolute lymphocyte count $< 800/\mu\text{L}$;
 - Hemoglobin < 10 g/dL.
19. Consideration by the Investigator, for any reason, that the subject is an unsuitable candidate to receive ABT-494 (upadacitinib) or participate in this study.
20. For subjects in Japan only: Positive result of beta-D-glucan (screening for pneumocystis jiroveci infection).

Rationale for Exclusion Criteria

1 – 7, 9	To select the appropriate subject population
8, 10 – 15, 18 – 20	To ensure safety of the subjects throughout the study
16, 17	ABT-494 is teratogenic in both rats and rabbits. The impact of ABT-494 on pregnancies is unknown

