5.2.4 Contraception Recommendations

Contraception Recommendation for Females

A woman who is postmenopausal or permanently surgically sterile (bilateral oophorectomy, bilateral salpingectomy or hysterectomy) is not considered to be a woman of childbearing potential and is not required to follow contraception recommendations.

Postmenopausal is defined as:

- Age \geq 55 years with no menses for 12 or more months without an alternative medical cause; or
- Age < 55 years with no menses for 12 or more months without an alternative medical cause AND a follicle-stimulating hormone (FSH) level > 40 IU/L.

If the female subject is < 55 years of age:

AND has had no menses for \geq 12 months AND has no history of permanent surgical sterilization (defined above), FSH should be tested at Screening.

- If FSH is not tested, it is assumed that the subject is of childbearing potential and protocol-specified contraception is required.
- If the FSH is tested and the result is consistent with post-menopausal status, contraception is not required.

- If the FSH is tested and the result is consistent with pre-menopausal status, contraception is required, and a serum pregnancy test must be performed (see Section 5.3.1.1 pregnancy test).

For a female subject at any age:

- Female subjects with menses within the past 12 months are of childbearing potential and FSH is therefore not required but contraception is required.
- Female subject who are surgically sterile (defined above) are not of childbearing potential and therefore no FSH testing or contraception is required.

A woman who does not meet the definition of postmenopausal or permanently surgically sterile is considered of childbearing potential and is required to practice at least one of the following highly effective methods of birth control that is effective from Study Day 1 (or earlier) through at least 30 days after the last dose of study drug.

- Combined (estrogen and progestogen containing) hormonal contraception (oral, intravaginal, transdermal) associated with the inhibition of ovulation, initiated at least 30 days prior to Baseline Visit.
- Progestogen-only hormonal contraception (oral, injectable, implantable) associated with inhibition of ovulation, initiated at least 30 days prior to Baseline Visit.
- Bilateral tubal occlusion/ligation (Japan only: bilateral tubal ligation only).

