- If the baseline urine pregnancy test performed at the site is negative, then dosing with study drug may begin. If the baseline urine pregnancy test performed at the site is positive, dosing with study drug must be withheld and a serum pregnancy test is required. The serum pregnancy test will be sent to and performed by the central laboratory. If the serum pregnancy test is positive, study drug must be withheld and the subject must be discontinued from the study. In the event a pregnancy test comes back borderline, a repeat test is required.
- If a urine pregnancy test post baseline is positive, study drug needs to be temporarily discontinued and a serum pregnancy test is required. The serum pregnancy test will be sent to and performed by the central laboratory. If the serum pregnancy test is positive, study drug must be permanently discontinued.

In Period 2, for women of childbearing potential, a urine pregnancy test will be performed at all visits and monthly at home between scheduled study visits (at Weeks 28 and 36 at home, unless an on-site visit is necessary due to rescue therapy with topical corticosteroids per Section 5.2.3.4). The results of the monthly at home tests will be communicated to the site. If a urine pregnancy test is positive, the subject must stop dosing, come in to the clinic and have blood drawn for a serum pregnancy test that will be analyzed at the central laboratory.

At each visit, the study staff should review the pregnancy avoidance recommendations with each subject of childbearing potential and male subjects with a partner of childbearing potential, and document this discussion in the subject's source records.

A pregnant or breastfeeding female will not be eligible for participation or continuation in this study.

Clinical Laboratory Tests

Blood and urine samples will be obtained for clinical laboratory tests listed in [Table 4](#). Samples will be obtained at the designated study visits in [Table 2](#).

Unscheduled clinical labs may be obtained at any time during the study if deemed appropriate per Investigator's discretion. A certified central laboratory will be utilized to process and provide results for the clinical laboratory tests. All abnormal laboratory tests that are considered clinically significant by the investigator will be followed to a satisfactory resolution.

The central laboratory chosen for this study will provide instructions regarding the collection, processing, and shipping of these samples.

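### Appendix P (Canada) prints the postmenopausal FSH cut-off for women under 55 in mIU/L instead of IU/L, a threshold 1000 times too low for exemption from contraception

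*Protocol*

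**What the plan says.** Protocol Section 5.2.4 gives two routes to postmenopausal status. From age 55, 12 months without menses and without another medical cause is enough. Below 55 the same history is needed, "AND a follicle-stimulating hormone (FSH) level > 40 IU/L". The section then covers the other outcomes: "If the FSH is tested and the result is consistent with pre-menopausal status, contraception is required", and "If FSH is not tested, it is assumed that the subject is of childbearing potential and protocol-specified contraception is required".

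Appendix P reprints the female contraception rules for Canada under the heading of Section 5.2.4. The age limit, the 12 months and the exclusion of other causes are the same, but the laboratory condition reads "AND an FSH level $>$ 40 mIU/L". A woman who meets the definition "is not considered to be a woman of childbearing potential and is not required to follow contraception recommendations"; one who does not "is required to use two forms of contraception", one highly effective and one effective. The appendix does not repeat the lines on an untested or pre-menopausal FSH.

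The rationale for the exclusion criteria in Section 5.2.2 states that "ABT-494 is teratogenic in both rats and rabbits". In Period 2, under Section 5.3.1.1, "for women of childbearing potential, a urine pregnancy test will be performed at all visits and monthly at home between scheduled study visits"; the home tests named are those at Weeks 28 and 36.

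**The concern.** The two places define the same term with the same number and different units. The difference runs in the unsafe direction: the appendix makes it easier to be classed as postmenopausal, although its contraception rules are otherwise the stricter ones (two methods in Canada, at least one elsewhere).

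This is an operative threshold. It decides which women under 55 may take study drug without contraception in a study with treatment up to Week 88. The appendix gives its own full definition and its own exemption sentence, so a Canadian site could reasonably work from it alone.

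**Working it through.** **Inputs**

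- Section 5.2.4: FSH > 40 IU/L, women under 55.
- Appendix P: FSH > 40 mIU/L, women under 55.
- Contraceptive methods required in Canada: 2 if of childbearing potential, 0 if postmenopausal (Appendix P).
- Contraceptive methods required under Section 5.2.4: at least 1 if of childbearing potential, 0 if postmenopausal.
- Named home urine tests, women of childbearing potential only: Weeks 28 and 36, so 2 (Table 2 note o and Section 5.3.1.1).

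**Conversion**

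1. Appendix P as printed: 40 mIU/L ÷ 1000 mIU per IU = 0.04 IU/L.
2. Ratio of the two cut-offs: 40 IU/L ÷ 0.04 IU/L = 1000.
3. If mIU/mL was meant: 40 mIU/mL × 1000 mL/L ÷ 1000 mIU per IU = 40 IU/L, which is exactly the Section 5.2.4 value.

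**Where the definitions disagree** (woman under 55, at least 12 months without menses, no alternative medical cause)

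| FSH (IU/L) | Section 5.2.4 | Appendix P as printed |
|---|---|---|
| ≤ 0.04 | childbearing potential | childbearing potential |
| > 0.04 to 40 | childbearing potential | postmenopausal |
| > 40 | postmenopausal | postmenopausal |

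**Consequence for a woman in the middle row, if a site applies the printed unit**

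| How Appendix P is read | Methods required | Home tests at Weeks 28 and 36 |
|---|---|---|
| Unit corrected | 2 | 2 |
| Appendix adds to Section 5.2.4 | 1, because Section 5.2.4 still applies | 2 |
| Appendix replaces Section 5.2.4 | 0 | 0 |

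**Which text is wrong.** The documents prove the conflict; that the appendix carries the error is an inference. The number is the same, a one-letter change from mIU/L to mIU/mL restores exact agreement, and no reason is given for a different Canadian value. Appendix P is current text, and the list of changes in Appendix Q does not touch it.

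**Pregnancy testing that remains.** Inclusion criterion 6 and Table 4 note d give the Screening serum test to all female subjects, so that safeguard stands. Later tests are less certain. For the Week 88 or premature-discontinuation serum test, Table 2 note m says all females, while the pregnancy-test text in Section 5.3.1.1 says women of childbearing potential. For on-site urine tests, Table 4 note h says all female subjects at Baseline and every later visit, while Table 2 note n and Section 5.3.1.1 again limit them to women of childbearing potential.

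**The case against.** The conflict itself is not in dispute. The case on the other side is about its practical size.

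- **Additive reading.** Inclusion criterion 7 and Section 5.2.4 introduce Appendix P as a source of further local requirements. On that reading Section 5.2.4 still binds Canadian sites, and the loss is one method and no home test. This stands as a limit on the consequence, but the printed threshold is still wrong and the protocol still holds two contradictory definitions. No rule says which prevails, and the appendix's self-contained restatement makes replacement a plausible reading.
- **Other controls in Section 5.2.4.** A result consistent with pre-menopausal status triggers contraception and a serum pregnancy test, and an untested FSH counts as childbearing potential. FSH is a central-laboratory test, so the site sees a reported value, and an experienced site would probably recognise the slip. This makes an actual error unlikely. Appendix P repeats neither rule, however, so a site working only from it would not meet them.
- **On-site urine tests.** Table 4 note h may keep these for every female subject. That would detect a pregnancy; it would not prevent one, and the protocol contradicts itself on who is tested.
- **Timing.** FSH is classified at Screening. SAP Appendix B Section 10.5 says the DLQI device error, corrected in August, affected the baseline of all subjects. The SAP is dated 23 August 2017 and the protocol synopsis 30 August 2017, so enrolment appears complete. If so, the corrected text would classify few or no new women, and the look-up of existing results is the part with practical value.
- **Small group.** Someone is affected only if she is Canadian, under 55, without menses for at least 12 months, has FSH of 40 IU/L or below, and is at a site that applied the printed unit. That group may be empty.

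**Conclusion.** The concern holds. Appendix P prints a cut-off of 0.04 IU/L where Section 5.2.4 has 40 IU/L, a factor of 1000 in the lax direction, in the rule that exempts women from contraception.

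The worst case for one woman is a fall from two required methods to none, with both named home tests lost. It assumes that the site treats Appendix P as replacing Section 5.2.4 and takes the unit literally; on the additive reading the fall is from two methods to one. The documents do not say how many women are affected, and the number may be zero. Sample size, power, alpha and the efficacy analyses are unaffected.

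This is a unit slip, but in a reproductive-safety threshold, and it should be corrected. Relying on sites to notice it is not an adequate control.

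**What to change.** In the next amendment, change the Appendix P cut-off to > 40 IU/L (equivalently > 40 mIU/mL) so that it matches Section 5.2.4.

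Also compare the screening FSH of every Canadian woman under 55 who was classed as postmenopausal on FSH with 40 IU/L. Any woman at or below it should be treated as of childbearing potential, with the Canadian two-method rule and the full pregnancy-test schedule. For women still on drug this remains useful, because contraception is required until at least 30 days after the last dose.

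The cost is one unit in the text and a look-up. Table 4 note g already schedules FSH at Screening for female subjects under 55, so no new samples are needed.
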